5.5 BIOBANKING

Not applicable.

5.6 **OTHER ASSESSMENTS**

Proprietary confidential information © 2021 Boehringer Ingelheim International GmbH or one or more of its affiliated companies

5.7 APPROPRIATENESS OF MEASUREMENTS

The primary endpoint measurements will be consistent with the recognized standard for symptomatic ambulatory patients with COVID-19.

All other measurements performed during this trial are standard measurements and will be performed in order to determine the efficacy and safety in an appropriate way.

Therefore, the appropriateness of all measurements applied in this trial is given.

6. INVESTIGATIONAL PLAN

The trial consists of three periods, a screening period, single dose treatment and a follow-up period.

In Phase II, randomised patients will receive a single dose of BI 767551 or placebo as infusion or inhalation. In Phase III, randomized patients will receive a single dose of BI 767551 or placebo as infusion or inhalation.

All required procedures are described in the Flowchart and in Sections 6.2.

After single treatment patients will be followed-up on Day 3,4,8,11,15,22, 29 and Day 91 / EOS visit.

6.1 **VISIT SCHEDULE**

No study procedures may be initiated prior to the patient or patient's legally acceptable representative signing the informed consent.

All subjects are to adhere to the visit schedule as specified in the Flowchart. Each visit date (with its window) is to be counted from Day 1 (Visit 2 date = visit with first IMP administration). If any visit has to be rescheduled, subsequent visits should be calculated again from Day 1.

Additional visits for the purpose of re-testing of laboratory parameters or AE monitoring may be included as deemed necessary by the investigator.

6.2 DETAILS OF TRIAL PROCEDURES AT SELECTED VISITS

Study procedures to be performed at each visit are listed in the flowchart and the respective protocol sections. Additional details on procedures at selected visits are provided below.

At all applicable visits vital signs should be collected prior to blood sampling.

NP swabs will be obtained by inserting a swab in one nostril along the nasal septum to the nasopharynx until resistance is felt, reaching a depth that is proximately the length from the outer nostril opening to the ear. Once resistance is felt, the swab will be left in place for a few seconds to allow for absorption of secretions and is slowly removed while rotating. OP swabs will be obtained by swabbing the posterior pharynx and tonsillar areas. Care should be taken to avoid accidental swabbing of the gums, tongue, or teeth. SARS-CoV-2 RNA levels will be determined from frozen (-80°C) transport medium using a clinically validated quantitative reverse-transcripase real-time PCR assay (RT-qPCR) assay. Results will be provided as Ct (Cycle threshold) values as well as quantitatively (copies/ml) based on a reference standard. These assays will be performed at central laboratory.

On days without an in-person visit, the anterior swabs will be self-collected by the patient on their own same time every day, when completing the study diary and temperature measurement. Patients will turn in their self-collected (remote) swabs at their next in-person visit.

6.2.1 Screening and run-in period(s)

Screening Period

Once the patient has consented, the patient is considered to be enrolled in the trial. The patient should be recorded on the enrollment log and be registered in the IRT. Each patient will be assigned a unique patient number, via the IRT system and enrollment will be recorded in eCRF. For the schedule of assessments and procedures during the screening period refer to the Flowchart.

During the screening visit, demographics information will be collected. This includes:

- age on the day of informed consent (in years)
- Sex (male, female in order to describe the subject's sex at birth),
- For women: of childbearing potential yes / no in order to characterize the patient population and as a basis for contraception requirements
- Ethnicity and race in order to sufficiently characterize the patient population, to support possible subgroup analyses if needed and to support the calculation of the kidney function via the CKD EPI formula unless not acceptable according to local regulations.

Study requirements, including the procedure for the follow-up of prematurely withdrawn patients must be fully explained to the patient and written informed consent obtained prior to initiating any study-related evaluation. The importance of staying in the trial until completion of all study requirements will be emphasized. No trial procedures should be done unless the patient has consented to taking part in the trial.

SARS-CoV-2 infection documentation is recorded on the eCRF. Positive RT-qPCR or antigen test will be obtained prior to randomisation. Documentation of laboratory-confirmed SARS-CoV-2 infection as determined by molecular test from any respiratory tract specimen (NP, nasal swab or saliva) is also acceptable.

Patients will be asked about their first symptoms related to COVID-19 and their current symptoms. The time of symptom onset should be recorded.

Urine pregnancy testing should be done prior to administration of study drug for all women of childbearing potential. Study drug should only be administered in case of a negative test result.

Medical History:

The current medical history of the patient may not be sufficient to confirm eligibility for the trial and the investigator may need to request previous medical histories and evidence of any

Boehringer Ingelheim		
BI Trial No.: 1487-0001		20 Apr 2021
c33563257-02	Clinical Trial Protocol	Page 79 of 127

diagnostic tests. In this case, the investigator must make at least one documented attempt to retrieve previous medical records. If this fails, a verbal history from the patient or his legal representative, documented in their medical records, would be acceptable. Medical history includes estimated date and time of first SARS-CoV-2 infection symptoms as well as symptom details.

Information on clinically significant previous and concomitant illnesses, or any clinically significant signs or symptoms that are present before informed consent, or pre-existing conditions identified through findings from assessments and examinations done during the screening visits will be recorded as medical history at screening.

Patients who do not meet eligibility critera should be documented as a screen failure. The patient must be registered as a screen failure in IRT system.

Re-screening

Re-screening of a previously screen failed patient will be permited once. Patients who have or RT-qPCR or antigen SARS-CoV-2 test within the screening window with a value outside the range specified by the inclusion criteria may have the test repeated once to determine eligibility. The RT-qPCR or antigen SARS-CoV-2 re-test performed must be the same test method used for initial screening and the result must be available within the screening window, prior to Visit 2 (Day 1). All remaining eligibility criteria must also be met. In case of re-screening patient will obtain new patient number per IRT.

If a patient is enrolled in error (does not meet all inclusion criteria or meets one or more exclusion criteria on the day of enrolment), the sponsor should be contacted immediately.

Baseline Conditions

Baseline conditions include a number of co-morbidities (e.g. respiratory, cardiovascular, metabolic, malignancy, endocrine, gastrointestinal, immunologic and renal).

In addition, as noted in Section 5.2.6.1. if any worsening of the underlying disease or of other pre-existing conditions or changes in vital signs, physical examination and laboratory test results, as judged clinically relevant by the investigator already exist prior to trial inclusion, they will be considered as baseline conditions and should be collected in the eCRF only.

6.2.2 Treatment Period(s)

The patient is randomised (Day 1; Visit 2) not later than 3 days after information consent upon confirmation of the eligibility criteria via IRT. Study medication dispensing and administration can occur on the same day (Day 1).

For the schedule of assessments and procedures during the treatment period refer to the Flowchart.

For Dosing and Treatment schedule please refer to Section 4.1.

The below procedures should be completed in the following order prior to trial drug administration. Those listed as optional do not need to be repeated when Visit 1 and Visit 2 are performed on the same day.

- Review of eligibility criteria (optional)
- SARS-Cov-2 symptoms review (optional)
- 11-point WHO Clinical progression scale (optional)
- Medical History (optional)
- Physical examination (optional)
- Vital signs
- Safety blood and urine samples collection
- Serum pregnancy test (see below for details on pregnancy testing)
- Blood samples for inflammatory and coagulation markers
- •
- NP swabs will be collected by site staff (If Visit 2 occurs on the same day as Visit 1 and the sample collected for screening was NP or nasal, the Visit 2 NP sample should preferably be taken from the other nostril). Care must be taken to ensure one (1) sample is taken at screening for eligibility and the second sample is taken as part of V2 procedures.
- •
- Dispensing of study diary
- IRT call (Phase II only: weight needed in IRT for weight-based dosing)

The patient will be monitored for possible infusion reactions and inhalation related reactions (bronchospasm) at the site for approximately 2 hours following study drug administration.

Vital signs will be assessed pre-dose, at end of infusion, and at approximately 2 hours after study drug administration. See Section 5.2.2.

Symptom targeted physical examination will be performed on day of treatment (if V1 and V2 are performed on separate days). See Section 5.2.1

Blood sampling shall be done prior to study drug administration. Patients do not have to be fasted for the blood sampling for the safety laboratory.

Pregnancy test for women of childbearing potential only. Negative urine pregnancy test must be confirmed prior to study drug administration. Serum test required at Visit 2. In case remote visits

are planned during the follow-up period, clinical site may provide subjects with at-home urine pregnancy test kits (may be sponsor-provided).

NP swabs will be taken by study staff for SARS-CoV-2 testing prior to IMP administration.

On day of treatment, participants will complete the study diary with site staff prior to IMP administration. Participant's answers will be recorded into the eCRFs. Participants will be asked to complete the diary at approximately the same time every day.

Participants will be given a thermometer and pulse oximeter to record their temperature and oxygen saturation each day in the diary.

Sites will capture information for a secondary contact that the site can contact if the participant cannot be reached (e.g. spouse, friend, neighbour). Contact information for secondary contacts will not be recorded in the eCRF

Concomitant medication review

Data concerning concomitant medications will be collected throughout the trial, as specified in the Flowchart.

Adverse event review is to be done at every visit, see Section 5.2.6 for more details.

6.2.3 Follow-up period and trial completion

Patients will be followed after treatment period up to Day 91. Follow-up period consists of 8 visits: Days 3,4,8,11,15,22,29 and Day 91 /EOS visit.

For the schedule of assessments and procedures during the follow-up period refer to the Flow chart. Sites will review with patient if there are any updates to the information provided for their secondary contact. Contact information will not be recorded in the eCRF

Participants will complete a study diary by recording their temperature, oxygen saturation and completing all questions every day up to protocol Day 29 (within the visit window). On days with a clinic or remote visit, patients will be reminded to complete all entries every day (preferably the same time every day) and to bring their diary with them to the next clinic visit. Clinic visit diary entry may also be completed at the clinic. In case of remote visits, every effort should be made to retrieve the study diary answers (or a copy of the answers), otherwise retrieve

the study diary from the participant at the next clinic visit. Guidance for reviewing and data entry of the participant's answers will be provided in the ISF.

NP swabs will be collected during in-patient visits as per Flowchart by site staff.

Symptom targeted physical examination will be performed up to Day 91. Weight will be collected at Days 29 and 91.

Vital signs measurements shall include blood pressure measurement, body temperature, respiratory rate, pulse rate and resting peripheral oxygen saturation. Measurements shall be performed before blood sampling at each clinic visit until Day 29.

Blood samples for haematology and chemistry will be collected at timepoints indicated in the Flowchart. For women of childbearing potential urine pregnancy tests will be performed at timepoints indicated in the Flowchart. In case urine pregnancy test positivity, serum pregnancy test shall be performed as well.

Blood samples (plasma and serum) for inflammatory and coagulation markers will be collected at time points indicated in the Flowchart.

Concomitant therapy information is to be collected at each visit, during on site visit or per telephone or e-mail during remote visits until Day 91 and at last visit in case patient discontinues the trial prematurely before completion Day 29.

AEs/SAEs collection shall be performed until Day 91 and at last visit in case patient discontinues the trial prematurely before completion Day 29.

If needed in the opinion of the investigator, after the EoS (End of Trial) visit additional visits may be scheduled for continued safety monitoring.

Abnormal assessments or lab values judged clinically relevant by the investigator will be monitored until they returned to a medically acceptable level.

Vital status information is to be collected for each patient that completes the EOS visit. In case patient discontinues the trial prematurely before their scheduled EOS visit, vital status information and information whether the patient has been hospitalized shall be collected at planned completion date of each individual patient. Any locally approved means of vital status information collection is accepted.

Early treatment discontinuation

In case the infusion or inhalation of study drug is permanenty discontinued before the whole amount of prepared solution has been administered to the patient, drug administration will not be re-initiated. Patients should be encouraged to follow all study procedures until their individual EOS visit. Given the patient's agreement, the patient will undergo the procedures for early treatment discontinuation (see Section 3.3.4.1) and follow up as outlined in the Flowchart (and Section 6.2.3).

Trial completion:

Trial completion is defined as a patient having reached the EOS visit. EOS visit will be at Week 12, Day 91.

7. STATISTICAL METHODS AND DETERMINATION OF SAMPLE SIZE

Phase II of the study is exploratory in nature. Phase III has a group-sequential design with two planned interim analyses. Further details about the interim analyses can be found in Section 7.2.8. The methods to control the global overall significance level for the primary endpoint are described in Section 7.1. Sample size calculations and information on the O'Brien and Fleming local nominal alpha levels for the different interim analyses and the final analysis and the probabilities of stopping the trial at an interim analysis or at the final analysis are summarized in Table 7.5.2:1.

7.1 NULL AND ALTERNATIVE HYPOTHESES

In Phase II, no confirmatory testing is performed and hence no null and alternative hypotheses are defined. All p-values are to be understood as exploratory. A justification of the sample size is provided in Section 7.5.1.

In Phase III, the superiority of BI 767551 compared to placebo will be tested for the proportion of patients hospitalized or who died from any cause by Day 29.

The null hypothesis is:

H0: The probability to get hospitalized or to die by Day 29 in the BI 767551 arm is equal to the probability to get hospitalized or to die by Day 29 in the placebo arm.

The alternative hypothesis is:

H1: The probability to get hospitalized or to die by Day 29 in the BI 767551 arm is smaller than the probability to get hospitalized or to died by Day 29 in the placebo arm.

The control of the global overall significance level of 2.5% (one-sided) is assured for the primary endpoint as follows: Adjustments accounting for the planned interim analyses are done using the Lan-DeMets spending function approach with an O'Brien and Fleming boundary. For the primary endpoint, statistical significance will be declared (either at one of the interim analyses or in the final analysis) if the analysis is significant at the local nominal one-sided alpha level. These O'Brien and Fleming local nominal one-sided alpha levels are given in Table 7.5.2:1 for each interim and the final analysis for the planned information fraction. The one-sided p-value is required for the primary endpoint due to the use of a group sequential design.

7.2 PLANNED ANALYSES

7.2.1 General considerations

In Phase II, efficacy analyses will be based on all randomised patients that have been treated.

Boehringer Ingelheim		
BI Trial No.: 1487-0001		20 Apr 2021
c33563257-02	Clinical Trial Protocol	Page 85 of 127

In Phase III, efficacy analyses will follow the intention-to-treat principle and will include all randomised patients whether the patient is treated with the study medication or not. For the confirmatory analysis of the primary endpoint of Phase III of the study, only the data of the patients randomised in Phase III will be included.

Safety analyses will include all treated patients who are documented to have taken any dose of the study medication and will be reported separately for Phase II and Phase III patients, as well as integrated across both parts where possible.

In Phase II, all analyses will be based on the treatment group as treated. In Phase III, all analyses will be based on the treatment group as randomised by IRT.

Although there is no per protocol data set in the study, reasons for important protocol deviations will be specified in the TSAP. Patients with important protocol deviations will be identified at Review Planning Meetings and listed in the CTR.

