4.3 TREATMENT COMPLIANCE

Study medication will be administered in accordance with the protocol, under supervision of the investigating physician or a designee at the site. At the time of study medication administered, the date, time and route(s) will be entered into the eCRFs.

The only reasons for deviations from the treatment schedule in the protocol would be due to the rare events of dosing mistakes or damaged treatment kits.

Clinical Trial Protocol

Proprietary confidential information © 2021 Boehringer Ingelheim International GmbH or one or more of its affiliated companies

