7.2.6 Safety analyses

Adverse events will be coded using the Medical Dictionary for Drug Regulatory Activities (MedDRA). Standard BI summary tables and listings will be produced. All adverse events with an onset between start of treatment and end of the REP, a period of 90 days after the last dose of trial medication, will be assigned to the on-treatment period for evaluation.

All treated patients will be included in the safety analysis. In general, safety analyses will be descriptive in nature and will be based on BI standards. No hypothesis testing is planned.

Statistical analysis and reporting of adverse events will concentrate on treatment-emergent adverse events, i.e. all adverse events occurring between start of treatment and end of the REP. Adverse events that start before first drug intake and deteriorate under treatment will also be considered as 'treatment-emergent'.

Frequency, severity (as graded according to DAIDS Table 5.2.6.1.5:1 [R21-0379]), and causal relationship of adverse events will be tabulated by system organ class and preferred term after coding according to the current version of the Medical Dictionary for Drug Regulatory Activities (MedDRA) at database lock.

Laboratory data will be analysed both quantitatively as well as qualitatively. The latter will be done via comparison of laboratory data to their reference ranges. Values outside the reference range as well as values defined as clinically relevant will be summarised. Treatment groups will be compared descriptively with regard to distribution parameters as well as with regard to frequency and percentage of patients with abnormal values or clinically relevant abnormal values.

Vital signs, physical examinations, or other safety-relevant data observed at screening, baseline, during the course of the trial and at the end-of-trial evaluation will be assessed with regard to possible changes compared to findings before start of treatment.

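### Phase III safety would be tabulated by randomised arm and Phase II safety by treatment received, so a patient given the wrong product is counted in the wrong arm and the integrated tables combine two rules

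*Protocol*

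**What the plan says.** Protocol Section 7.2.1 sets one assignment rule per phase. For Phase II: "In Phase II, all analyses will be based on the treatment group as treated". For Phase III: "In Phase III, all analyses will be based on the treatment group as randomised by IRT". Both cover every analysis; neither is limited to efficacy.

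The paragraph just before these sentences defines the safety population by exposure: "Safety analyses will include all treated patients who are documented to have taken any dose of the study medication". It says safety will be reported for each phase and "as well as integrated across both parts where possible".

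Section 7.2.6 repeats the population ("All treated patients will be included in the safety analysis") and says that "safety analyses will be descriptive in nature and will be based on BI standards". It does not say in which arm a patient is counted. Section 4.3 accepts that departures from the treatment schedule may arise from "rare events of dosing mistakes or damaged treatment kits".

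The SAP covers Phase II only (SAP Section 3). It repeats the treatment-received rule (SAP Section 7) and gives no rule for Phase III.

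**The concern.** Assignment by randomised arm protects the comparison of efficacy. For safety, the question is what happened to people exposed to the drug, so the usual convention is to classify by treatment received. The plan follows that convention when deciding who enters the safety set, but in Phase III not when deciding which column the patient appears in.

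Two things follow. First, a placebo-randomised patient who receives active drug by mistake has any infusion or hypersensitivity reaction counted as a placebo event, which pulls the arms together. Second, the integrated tables have no single definition of treatment group, because Phase II patients enter by product received and Phase III patients by allocation.

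What is at stake is the safety table of a trial that Protocol Section 1.3 describes as potentially pivotal for registration, for an antibody whose safety profile Section 1.2.6 says is not yet established. Hypersensitivity and inhalation-related bronchospasm are adverse events of special interest (Section 5.2.6.1.4).

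**Working it through.** No figure in the documents depends on this rule, so the first check is one of reading; the arithmetic only sizes the effect.

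**Does the Phase III rule include safety?** Section 7.2.1 describes the Phase II efficacy analyses, then the Phase III efficacy analyses, then the safety analyses, and then gives the assignment rules for all analyses. The narrower term, efficacy analyses, is used earlier in the same section and not in the rule. On its wording, the rule includes safety.

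**Does anything override it?**

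| Place | Who is included | Which arm |
|---|---|---|
| Protocol 7.2.1, Phase II | treated patients | treatment received |
| Protocol 7.2.1, Phase III safety | treated patients | as randomised |
| Protocol 7.2.1, integrated safety | both parts | not stated |
| Protocol 7.2.6 | treated patients | not stated |
| SAP 7 and 7.8 (Phase II only) | treated set | treatment received |

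Nothing replaces the Phase III rule for safety, and nothing sets a rule for the integrated tables.

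**Size of one misplaced event.** Inputs: about 1300 patients in Phase III, randomised 1:1 (Protocol synopsis and Section 7.5.2), so 650 per arm.

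- Shift in one arm: 1/650 = 0.15 percentage points.
- Moving an event from active to placebo lowers one arm and raises the other, so the difference changes by about 2/650 = 0.31 points.
- Illustration: two true drug reactions, one of them in a placebo-randomised patient given active drug. By treatment received the count is 2 versus 0; as randomised it is 1 versus 1.

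**Average dilution.** Let a share s of each arm receive the other arm's product, with event risks p_a on active and p_p on placebo.

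- Active arm as randomised: (1 − s)p_a + s·p_p
- Placebo arm as randomised: (1 − s)p_p + s·p_a
- Difference as randomised: (1 − 2s)(p_a − p_p)

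The documents give neither a mis-dosing rate nor adverse event rates. Assume p_a = 5% and p_p = 2%, a difference of 3.00 points by treatment received, and a range for s:

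| s | Patients per arm counted in the wrong arm (650·s) | Difference as randomised (points) |
|---|---|---|
| 0.2% | 1.3 | 2.99 |
| 0.5% | 3.25 | 2.97 |
| 1% | 6.5 | 2.94 |
| 2% | 13 | 2.88 |

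**Expected number of misplaced rare reactions.** If r is the risk of a drug-specific reaction, the expected number in placebo-randomised patients given active drug is 650·s·r. With s assumed at 0.2% to 2% and r at 0.1% to 1%, this runs from 650 × 0.002 × 0.001 = 0.0013 to 650 × 0.02 × 0.01 = 0.13 for the whole of Phase III.

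**The case against.** The strongest case on the other side accepts the literal reading and argues that little follows from it.

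- **Few patients are affected.** The two rules differ only for a patient who receives the other arm's product; a partial dose of the assigned product stays in the right arm. Section 4.3 calls dosing errors rare and does not say that they involve the wrong arm. Treatment is a single supervised dose assigned through IRT. This stands, and it limits the size.
- **A misplaced anaphylaxis needs two rare events in one patient.** This also stands: the expected number above is at most 0.13 under the assumed ranges.
- **Other safeguards exist.** Important protocol deviations are listed in the trial report, each event of special interest goes to the sponsor within 24 hours, and the DMC sees unblinded data. A single severe reaction would be examined as a case. Safety is descriptive, so no test or boundary turns on the rule. These points soften the consequence, but they do not change which arm the tables show.
- **The sponsor's standards or a Phase III SAP might have used treatment received.** Neither is available. If the standards do so, they conflict with Section 7.2.1, and the text still needs correcting.
- **The trial ended in Phase II.** The SAP reports 5 patients randomised and uses treatment received. No reported result is touched, but the protocol rule remains as written.

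**Conclusion.** The concern holds. As written, the protocol assigns Phase III safety data by randomised arm, and its integrated safety tables would combine that with Phase II data assigned by treatment received, with no rule for the pool. The conclusion rests on taking the all-analyses wording of Section 7.2.1 at face value; nothing in either document narrows it.

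The defect is minor. Average dilution is negligible at any plausible error rate, and the practical risk is confined to a rare drug-specific reaction appearing in the placebo column. The mis-dosing and event rates used to size it are assumptions. Because Phase III never started, the point matters for the quality of the plan and for any reuse of this text.

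**What to change.** In Protocol Section 7.2.1, limit the as-randomised sentence to Phase III efficacy analyses. Add one sentence saying that safety analyses in Phase II, in Phase III and in the integrated set classify patients by the treatment they actually received. Repeat the rule in Section 7.2.6, where the safety analysis is described and no assignment rule is given, and carry it into any Phase III SAP.

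The cost is the wording. The data needed are already to be recorded: Section 4.1.8 requires sites to document product use by patient, with code numbers linking product and patient. Phase III efficacy, the alpha allocation and the sample size are unchanged.
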